#### 7.4 JUSTIFICATION FOR SENSITIVE PROCEDURES

Not applicable.

#### 7.5 CONCOMITANT MEDICATIONS, TREATMENTS, AND PROCEDURES

Concomitant medications, treatments and procedures are those occurring from malaria inoculation until the end of the study (last visit). Those occurring prior to inoculation are classified as prior medications, treatments and procedures. Medications taken 28 days before the malaria inoculation will be recorded as prior medication. Prior and concomitant medications, treatments and procedures permitted in this study are outlined in the inclusion/exclusion criteria (Section 5.1 and 5.2).

On inoculation day, subjects will be questioned in relation to relevant aspects of compliance with the study protocol, including drug intake since their screening visit. Details of all other drugs taken (prescription and over-the-counter, systemic and topical administration) will be recorded at this time and appropriate action taken. The investigator may permit the use of ibuprofen up to 1.2 g/day or paracetamol up to 4 g/day, for treatment of headache or other pain if required. Ibuprofen is the preferred treatment for headache or pain. To minimise the risk of liver enzyme elevation paracetamol is to be avoided if possible, however paracetamol may be required by some subjects and as such is not a prohibited substance. Any medication taken from inoculation day to the end of the study (last visit), for treatment of a medical condition, is to be recorded in the concomitant medication pages in the eCRF. The exact dose and timing of each dose should be recorded.

##### 7.5.1 PRECAUTIONARY MEDICATIONS, TREATMENTS, AND PROCEDURES

Not applicable.

#### 7.6 PROHIBITED MEDICATIONS, TREATMENTS, AND PROCEDURES

Subjects will be informed and reminded of the following restrictions during recruitment, the informed consent process, and during screening and other assessments:

- Subjects should not consume grapefruit or Seville oranges from inoculation day until the end of the study.
- Subjects should not consume quinine containing foods/beverages such as tonic water, lemon bitter, from inoculation day until the end of the Riamet® treatment.
- Subjects should not eat any poppy seeds in the 24 hours before the following points: screening, inoculation day, and day of admission for OZ439 and PQP treatment.

- Subjects should not eat or drink any food or beverages that contain alcohol (e.g. beer, wine, and mixed drinks) during confinement at the clinical unit and also 24 hours prior to each alcohol breath test. Subjects should not drink more than 2 standard drinks per day from 24 hours before inoculation until the end of the Riamet® treatment.
- Subjects should not consume beverages that contain xanthine bases (e.g. Red Bull, coffee) during confinement at the clinical unit. Subjects should not consume more than 400 mg caffeine per day, equivalent to more than 4 cups of coffee, from inoculation until the end of the Riamet® treatment.
- Subjects should not use tobacco during confinement at the clinical unit. Subjects should not smoke more than 5 cigarettes or equivalent per day from inoculation until the end of the Riamet® treatment.

## 7.7 PROPHYLACTIC MEDICATIONS, TREATMENTS, AND PROCEDURES

Not applicable.

## 7.8 RESCUE MEDICATIONS, TREATMENTS, AND PROCEDURES

The rescue medications used in this study are Riamet® and Primacin™ (if required). See details in Section 6. If a subject vomits or cannot tolerate oral drugs, then artesunate will be administered intravenously as described in Section 6.1.5.

## 7.9 SUBJECT ACCESS TO STUDY AGENT AT STUDY CLOSURE

Not applicable.

# 8 ASSESSMENT OF SAFETY

## 8.1 SPECIFICATION OF SAFETY PARAMETERS

Safety of a single combined dose of OZ439 and PQP will be evaluated by the incidence, severity and relationship of observed and self-reported AE's, AESI's and SAE's. Other safety parameters monitored during this study include physical examination, vital signs, clinical biochemistry, haematology, urinalysis, triplicate ECG, serology, RBC alloantibody testing, and malaria clinical score. See Sections 7.1 and 7.2 for details of these procedures. All safety parameters will be recorded in the eCRF. Safety monitoring will be specified in a safety management plan.

### 8.1.1 DEFINITION OF AES (AE)

An AE is defined as any untoward medical occurrence, i.e., any unfavourable and unintended sign (including an abnormal laboratory finding), symptom or disease that occurs in a subject during the

course of the study and which does not necessarily have a causal relationship with this treatment (i.e., whether or not considered drug-related)

A treatment-emergent AE (TEAE) is an event that emerges following treatment with the investigational medicinal products (IMP) OZ439 and PQP, having been absent pre-treatment, or worsens relative to the pre-treatment state.

AEs include but are not limited to

- A new symptom, sign or medical condition.
- A disease or medical condition detected or diagnosed during the course of the study even though it may have been present prior to the start of the study.
- An exacerbation of a pre-existing medical condition or disease.
- An increase in frequency or intensity of a pre-existing episodic disease or medical condition.
- Continuous persistent disease symptoms present at study start that worsen following the start of the study.
- An abnormal assessment (e.g. change on physical examination, ECG findings) if it represents a clinically significant finding that was not present at study start or worsened during the course of the study.
- An abnormal laboratory test result if it represents a clinically significant finding, symptomatic or not, which was not present at study start or worsened during the course of the study or led to dose reduction, interruption or permanent discontinuation of study treatment.

Borderline abnormal laboratory findings and other objective assessments should NOT be routinely captured and reported as AEs, as they will be collected and analysed separately. However, abnormal laboratory findings or other objective measurements that meet the following criteria should be captured and reported in the AE section of the eCRF:

- the result meets the criteria for reporting as an SAE
- the test result is associated with accompanying symptoms, and/or
- it requires additional diagnostic testing or medical/surgical intervention, and/or
- it leads to a change in trial dosing, or discontinuation from the trial, significant additional concomitant drug treatment, or other therapy, and/or
- it is considered by the investigator or Sponsor to be clinically significant or represent a clinically significant change from baseline.

Merely repeating an abnormal test, in the absence of any of the above conditions, does not constitute an AE. Any abnormal test result that is determined to be an error does not require reporting as an AE.

Surgical procedures themselves are not AEs; they are therapeutic measures for conditions which may, or may not, be AEs.

Certain information, although not considered an AE, must be recorded, reported, and followed up as indicated for an SAE (see Section 8.4.2 Serious AE Reporting). This includes:

- Pregnancy exposure to an IMP. If a pregnancy is confirmed, use of the IMP must be discontinued immediately. Information about pregnancy exposure includes the entire course of pregnancy and delivery, and perinatal and neonatal outcomes, even if there are no abnormal findings. Both maternal and paternal exposures are considered other reportable information. For exposure involving the female partner of a male subject, the necessary information must be collected from the subject, while respecting the confidentiality of the partner.
- Lactation exposure to an IMP with or without an AE.
- Overdose of an IMP as specified in this protocol with or without an AE.
- Inadvertent or accidental exposure to an IMP with or without an AE

---

### 8.1.3 DEFINITION OF AES OF SPECIAL INTEREST (AESI)

An AESI (serious or non-serious) is one of scientific and medical concern specific to the sponsor's product or programme, for which ongoing monitoring and rapid communication by the Investigator to the sponsor could be appropriate. Such an event might require further investigation in order to characterise and understand it. Depending on the nature of the event, rapid communication by the trial sponsor to other parties (e.g., regulators) might also be warranted (CIOMS VI, ICH E2F, 2010). Any abnormalities listed below should be reported as AESI:

Hepatic:

- any ALT or AST above 5xULN
- an elevation in bilirubin 2xULN
- any AST or ALT above 2xULN and (TBL > 1.5x ULN or INR > 1.4)
- any AST or ALT above 2xULN with the appearance of fatigue, nausea, vomiting, right upper quadrant pain or tenderness, fever, rash and/or eosinophilia (eosinophil percent or count above the ULN)

Cardiac:

- QTcB or QTcF at any time >480ms
- bundle branch block (except right bundle branch block that was present prior to IMP administration)
- any arrhythmia except:
  - sinus bradycardia that is
    - clinically asymptomatic, and
    - not associated with any other relevant ECG abnormalities
  - sinus tachycardia that is
    - clinically asymptomatic, and
    - associated with a body temperature >38.0°C and
    - not associated with any other relevant ECG abnormalities
  - respiratory sinus arrhythmia,

- wandering atrial pacemaker,
- isolated, single premature atrial/ventricular complex (i.e. no bigeminy, trigeminy, couplets, triplets or salvos) that does not occur ~~more~~ once in a particular ECG tracing.

Haematological:

- HB drop >2.0 g/dL from baseline prior to inoculation
- Absolute neutrophil count ~~500~~/ $\mu$ l.
- Platelet count ~~75,000~~ /mm^3

Dermatological:\*

Clinical signs of possible cutaneous adverse reactions such as:

- dermatitis,
- rash,
- erythematous rash,
- macular rash,
- papular rash,
- maculopapular rash,
- pruritic rash,
- pustular rash,
- vesicular rash

\* if one of these cutaneous reaction is observed and when feasible, pictures of the lesions should be obtained

---

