#### Piperaquine phosphate (PQP) risks

PQP as a combination antimalarial with hydroartemisinin is well tolerated in both adults and children, with the main AEs reported being GI disturbances such as diarrhea [39, 40]. Studies with dihydroartemisinin/PQP demonstrated corrected QT (QTc) interval prolongation during treatment [41, 42]. Very few individual patients have been observed to have a prolongation that could be regarded as clinically significant (>60 msec); of note, the QTc prolongation induced by PQP has not been reported to be associated with clinically relevant cardiovascular events, would suggest a lack of pro-arrhythmic effect. Therefore, although statistically significant, the QTc prolongation observed following PQP therapy is unlikely to be of clinical concern. European regulatory authorities have advised that Eurartesim (dihydroartemisinin/PQP) not be administered with food to reduce PQP peak concentrations, and caution that pre- and post-electrocardiographic monitoring be undertaken, and avoidance of concomitant recent exposure to drugs at risk of QTc prolongation [18, 42, 43]. Therefore, during this study, subjects will receive PQP under fasting conditions and will have ECGs recorded before and after treatment.

PQP has been clinically well tolerated in previous IBSM studies using this drug [14]. In these studies, PQP treatment demonstrated a robust safety profile in doses up to 960 mg when used for the treatment of uncomplicated falciparum malaria infection.

Details on the safety and efficacy of PQP as part of the combination product Eufartesimbe found in the European Medicines Agency (EMA) European Public Assessment Report.

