### Medical history and clinical status

1. Haematology, clinical chemistry, coagulation or urinalysis results at screening or on admission prior to ~~on~~ inoculation or IMP administration that are outside of ~~Sponsor~~ approved clinically acceptable laboratory ranges documented in the laboratory manual are considered clinically relevant.
2. Any history of malaria or participation in a previous malaria challenge study.
3. Must not have travelled to or lived (>2 weeks) in a ~~malaria~~ endemic region during the past 12 months or planned travel to a ~~malaria~~ endemic region during the course of the study (for endemic regions see <https://map.ox.ac.uk/countryprofiles/#/>). Bali is not considered a ~~malaria~~ endemic region.
4. Participation in any investigational product study within the 12 weeks preceding ~~IMP~~ administration
5. Has evidence of increased cardiovascular ~~vascular~~ risk (defined as >10% ~~5~~ year risk for those greater than 35 years of ~~age~~ determined by the Australian Absolute Cardiovascular Disease Risk Calculator (<http://www.cvdcheck.org.au/>)). Risk factors include sex, age,

- systolic blood pressure (mm/Hg), smoking status, total and HDL cholesterol (mmol/L), and reported diabetes status.
6. Symptomatic postural hypotension at screening (two consecutive readings), or asymptomatic postural hypotension defined as a decrease in systolic blood pressure  $\geq 20$  mmHg within 2-3 minutes when changing from supine to standing position.
  7. History of splenectomy.
  8. History or presence of diagnosed (by an allergist/immunologist) or treated (by a physician) food or known drug allergies (including but not limited to allergy to any of the antimalarial rescue medications to be used in the study), or history of anaphylaxis or other severe allergic reactions. Note. Subjects with seasonal allergies/hay fever, house dust mite or allergy to animals that are untreated and asymptomatic at the time of dosing can be enrolled in the study.
  9. History of convulsion (including intravenous drug or vaccine-induced episodes) Note. A medical history of a single febrile convulsion during childhood is not an exclusion criterion.

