### Coagulation testing

Blood for PT, APTT and INR will be collected at screening visit.

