PQP: piperazine phosphate, EOS: End of Study, BDI: Beck Depression Inventory, ECG: electrocardiogram, G6PD: glucose-6-phosphate dehydrogenase, RBC: red blood cell, PK: pharmacokinetic, PD: pharmacodynamic, qPCR: quantitative polymerase chain reaction, qRT-PCR: reverse transcription qPCR

a An additional safety visit will occur between Day 0 and Day-1 to collect samples for haematology, biochemistry and urinalysis, unless screening laboratory assessments were conducted within this period.

b Daily visits until qPCR positive, and then twice daily visits until OZ439 and PQP treatment.

c Symptom-directed physical examination will be performed only if clinically indicated at the discretion of the investigator (see Appendix 3 for a list of symptoms and signs of malaria).

d Perform follicle stimulating hormone test (postmenopausal females) at screening.

e To be performed at screening visit

f May be performed at the investigator's discretion, most probably pre and post administration of rescue medication to measure the level of gametocytaemia.

g Cannulate subjects with an indwelling intravenous cannula for the malaria inoculum, and record which arm is utilised. Administer the malaria inoculum of ~2 800 viable *P. falciparum* 3D7 infected human RBCs intravenously in the morning (approximately 9:00 AM). Observe for a minimum of 60 minutes after inoculation to evaluate for immediate adverse reactions. Educate subjects on signs and symptoms of malaria (Appendix 3). Emphasise to subjects the importance of returning on the nominated day (approximately Day 8), or as advised by the clinical unit staff, for IMP antimalarial treatment. Provide subjects with diary cards and thermometers to record temperature readings during the study in the event of symptoms of fever. Subjects will also record symptoms and concomitant medications on the diary cards during the study.

h Riamet® treatment will occur on Day 2+2, or earlier if there is failure of clearance defined as failure to clear parasitaemia by at least 10-fold at 72 hours post-IMP administration or recrudescence of parasitaemia defined as  $\geq 5$  000 blood stage parasites/mL and a 2-fold increase within 48 hours, or a malaria clinical score of 6 at the investigator's discretion.

i Primacin™ treatment if required (Section 6.1.5)

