Appendix 2: Total blood volume

Procedure	Sample	Volume per sample (mL)	No. samples per subject	Total volume per subject (mL)
Laboratory Safety Assessment	Haematology (including G6PD)	2	7	14
		4	2	8
	Biochemistry /biomarker(may include Serology CRP,	5	6	30
		8.5	3	25.5
	Coagulation profile	2.7	1	2.7
	Safetyserum storage	5	2	10
RBC alloantibody	4	2	8	
Bioanalysis	PK analysis	4	21	84
Cannulation	Discard	2	19	38
Malaria Monitoring	Malaria 18S qPCR	2	36	72
	Parasite lifecycle stage qRT-PCR	2	2	4
Main study total (mL)				~297
Exploratory (optional)	ImmuneCell Characterisation	53	2	106
		26	3	78
	Complement Regulatory Proteins	2	8	16
Additional optional exploratory total(mL)				~203
Main study and exploratory components(mL)				~497

This table is indicative and may vary based on qPCR levels and safety follow-up samples. Additional blood samples may be taken for unscheduled safety and qPCR assessments as required by the Investigator, provided the total volume taken during the study does not exceed 450 mL during any period of 30 consecutive days.

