Additionally, a frequency table showing the liver enzyme elevation categories for the highest post-dose values will be prepared.

Vital signs

The following vital signs parameters are collected: supine heart rate, supine systolic (SBP) and diastolic blood pressure (DBP) and body temperature.

Low, normal, and high ranges for vital signs are defined in Table 5 below.

Table 5. Low, normal, and high ranges for vital signs

	Heart rate (bpm)	SBP (mmHg)	DBP (mmHg)	Temperature (°C)
Low	<40	<90	<45	<35.0
Normal	40-100	90-150	45-90	35.0-37.5
High	>100	>150	>90	>37.5

Vital signs parameters will be summarised by means of descriptive statistics at each analysis visit. Actual values and changes from baseline will be tabulated separately.

Abnormalities will be presented as cross-tabulations of the abnormality at each post-baseline analysis visit versus the baseline abnormality. Numbers of subjects with treatment-emergent abnormalities will also be shown.

All vital signs data will be listed. In addition, a listing will be provided showing only abnormal values and their baseline.

Electrocardiograms

All individual ECG parameter results (heart rate, PR interval, RR interval, QRS duration, QT interval, QTcB interval, QTcF interval) and the clinical assessment of the ECG will be presented in a data listing. ECG parameter values and changes from baseline will be summarised, using descriptive statistics, by treatment and visit. Where triplicate ECG evaluations were performed, the mean value for each subject (for the protocol specified time-point) will be used for the calculation of summary statistics. In addition, individual abnormal ECG results will be presented in a separate data listing.

The clinical assessment of the ECG (RR, PR, QRS, QT and QTcF intervals) will be presented in subject data listings.

Clinical assessment of the ECG (Normal, Abnormal NCS, Abnormal CS, Not Evaluable and Not Done) will also be summarized, by treatment, using frequency tabulations (number and percentage of subjects under each category). The normal ECG ranges once on study are in Table 6.

Table 6. ECG normal ranges

Parameter	Range
PR interval	<= to 210 msec
QRS	>50 to < = to 120 msec
QT interval	>200 to < 500 msec
QTcB/QTcF	Males: ≤ 450 msec
QTcB/QTcF	Females: ≤ 470s msec

Malaria clinical score

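### Two AESI criteria do not match the rest of the plan: no INR is scheduled after screening to feed the hepatic one, and the QTc one ignores change from baseline, which is how the protocol describes the risk

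*Protocol*

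**What the plan says.** **Hepatic criterion.** Protocol 8.1.3 lists four hepatic AESI criteria, and SAP 6.8 repeats them. One is "any AST or ALT above 2xULN and (TBL > 1.5x ULN or INR > 1.4".

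**Coagulation schedule.** Protocol 7.2.1 (Coagulation testing) states "Blood for PT, APTT and INR will be collected at screening visit". The Schedule of Events marks coagulation in the screening column only, with the footnote "To be performed at screening visit". Appendix 2 has one row, "Coagulation profile", with one 2.7 mL sample per subject. The SAP's own schedule (Table 4) has no coagulation row. Exclusion criterion 1 in Protocol 5.2, however, refers to "Haematology, clinical chemistry, coagulation or urinalysis results at screening or on admission prior to" inoculation or IMP administration, and no coagulation draw is scheduled at either of those points.

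**Cardiac criterion.** Protocol 8.1.3 gives "QTcB or QTcF at any time >480ms", and the SAP uses the same absolute limit.

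**How the protocol describes the QTc risk.** Section 2.3.1 reports changes. With OZ439 plus PQP most prolongations lay between 30 and 60 ms, and some in malaria patients exceeded 60 ms. The PQP paragraph says "Very few individual patients have been observed to have a prolongation that could be regarded as clinically significant (>60 msec"), then judges that the prolongation seen after PQP is not likely to matter clinically.

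**ECG analysis.** SAP 6.8 says "ECG parameter values and changes from baseline will be summarised, using descriptive statistics, by treatment and visit". It adds normal-range and clinical-assessment outputs, but no count of subjects by size of QTc change. SAP 6.1 generally keeps unscheduled and repeat values out of summary tables.

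**The concern.** AESI status is the objective route to rapid notice. Protocol 8.4.4 requires notification within 24 hours whether or not the event is serious, and the medical monitor and sponsor are then informed. Protocol 2.3.1 asks for close monitoring of both liver and cardiac function.

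An AESI criterion with no scheduled measurement gives a count that will tend to zero whatever happens to the subjects, and a reader of the AESI table cannot tell this from a true zero. An absolute QTc limit, in subjects admitted with normal QTc, is least sensitive to large rises in those with low baselines.

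The cardiac point is not remote. QTc prolongation was among the most frequent AEs in the Phase IIb study of OZ439 800 mg with PQP, and dose groups 2A (800/960 mg) and 3B (800/640 mg) use two of that study's dose combinations.

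**Working it through.** **1. Is any INR planned after screening?** Inputs are the main-study rows of Protocol Appendix 2 (volume x number of samples, mL):

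14 + 8 + 30 + 25.5 + 2.7 + 10 + 8 + 84 + 38 + 72 + 4 = 296.2

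This reproduces the stated total of about 297 mL. Within it there is 1 coagulation sample against 6 + 3 = 9 biochemistry/serology samples. The budget, the schedule and 7.2.1 agree, so no INR is planned after screening.

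**2. Which hepatic cases depend on INR alone?** Remove those that the other limbs catch with scheduled data:

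- ALT or AST above 5xULN: caught.
- Bilirubin 2xULN: caught.
- ALT or AST above 2xULN with total bilirubin above 1.5xULN: caught.
- ALT or AST above 2xULN with fatigue, nausea, vomiting, right upper quadrant pain or tenderness, fever, rash or eosinophilia: caught.

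What remains is ALT or AST above 2x and up to 5xULN, INR above 1.4, total bilirubin at or below 1.5xULN, and none of the listed symptoms or eosinophilia.

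**3. Which QTc rises escape the AESI limit?** Rise needed = 480 - baseline.

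| Baseline (ms) | Rise needed to be an AESI (ms) |
|---|---|
| 360 | >120 |
| 380 | >100 |
| 400 | >80 |
| 420 | >60 |
| 450 (entry ceiling, men) | >30 |
| 470 (entry ceiling, women) | >10 |

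A rise above 60 ms can stay at or below 480 ms only if baseline is below 480 - 60 = 420 ms. From 420 ms upward, every such rise is an AESI.

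**4. Do the on-study normal ranges catch it instead?** The limits are 450 ms (men) and 470 ms (women) in Protocol 7.1.1 and SAP Table 6. A rise above 60 ms stays inside the range if baseline is below 450 - 60 = 390 ms in men, or 470 - 60 = 410 ms in women. For example, 395 to 470 ms is a rise of 75 ms. In a woman it is neither an AESI nor out of range. In a man it is not an AESI, but it exceeds 450 ms and is flagged as abnormal.

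**5. How many subjects could be affected?** The documents give no baseline QTc distribution. Assume a normal distribution truncated at the entry ceiling, with mean 390 to 420 ms and SD 15 to 20 ms. The share with baseline at or below 420 ms is then about 50% to 98% (84% to 91% at mean 400). This is the share in whom a rise just over 60 ms would not trigger the AESI. It is not a forecast of how many will have such a rise.

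**The case against.** The strongest reply is that little is lost. Most of it stands, and it limits the point.

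- **INR.** A reader might infer that INR is never measured again and that the limb can never be met. The documents do not show that. Protocol 7.1.1 and 7.3.6 allow unscheduled safety tests and visits at discretion, and 7.2.1 requires significant deviations from screening to be followed up. What they show is that INR is not scheduled. Nor is hepatic surveillance disabled: three other criteria and the bilirubin limb work. Several of the listed symptoms (fatigue, nausea, vomiting, fever) are also malaria signs or symptoms, so the symptom limb may often apply in this infected cohort.
- **QTc reporting.** A reader might infer that a rise above 60 ms goes unreported. It does not have to. Protocol 7.1.1 sends clinically significant ECG findings to the medical monitor and sponsor and records them as AEs, and 8.1.1 covers clinically significant changes from baseline. What is missing is the AESI route, which does not depend on judgement.
- **The 60 ms figure.** It is tempting to say that the protocol declares such a rise clinically significant. The wording is conditional, comes from background on dihydroartemisinin/PQP, and is followed by reassurance. Nor does any passage say that the QTc criterion was meant to detect change. The same list does use change from baseline for haemoglobin, but that shows only that such a form was available.
- **Cohort reviews.** The SDRT is not confined to AESIs. Protocol 8.6 gives it clinical and laboratory safety data, AEs and SAEs.
- **Final reporting.** Listing 16.4.3 shows individual ECG changes, and the visit summaries include a maximum. With 2 or 4 subjects per dose group, a large rise can be found by inspection. The summaries still give no per-subject count across visits, and they generally omit unscheduled ECGs.

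**Conclusion.** Both gaps hold, at modest size.

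The hepatic INR limb has no scheduled data after screening. The uncovered case is the narrow one in step 2, and the practical harm is that a zero count could be read as absence.

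The QTc AESI criterion has no change-from-baseline limb, while the protocol's own risk description is in those terms. A rise above 60 ms from a baseline below 420 ms can fall outside the AESI list. From below 410 ms in women or 390 ms in men it can also stay inside the on-study normal range. The thresholds are exact arithmetic on the documents' limits and apply when both QTcB and QTcF stay at or below 480 ms. Only the share of subjects affected rests on an assumed baseline distribution.

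The documents do not support saying that INR was never measured, that such QTc rises cannot be reported, or that the SDRT would not see them.

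**What to change.** **INR.** Reconcile the INR criterion (Protocol 8.1.3, SAP 6.8) with the coagulation schedule (Protocol 7.2.1, 7.3.7, Appendix 2) and with exclusion criterion 1. How to do so is for the sponsor. Under Protocol 13.2 a change to study assessments is a substantial amendment needing ethics approval. The SAP already describes enrolment of 24 subjects in the past tense. If sampling is complete, state in the SAP and CSR that this limb was not systematically evaluable, and report how many subjects had any post-screening INR. This costs a sentence or two and one count.

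**QTc analysis.** In SAP 6.8 and Table 14.3.6.2b, add by dose group the number of subjects whose maximum post-dose QTcF increase from treatment baseline (mean of triplicate) exceeds 30 ms and 60 ms, the bands that Protocol 2.3.1 uses. Include unscheduled ECGs, as an explicit exception to SAP 6.1. State whether the post-dose window ends at rescue treatment or at end of study, since the SAP already separates those phases for AEs. This costs one table panel and needs no new ECGs.

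**QTc criterion.** Ask the sponsor to reconcile the absolute AESI limit (Protocol 8.1.3, SAP 6.8) with the change-from-baseline risk described in Protocol 2.3.1, and to record the reasoning. No threshold is proposed here.
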